8.1.10. Non-Serious Adverse Events of Special Interest

Adverse events potentially suggestive of distant spread of toxin effects are listed in Appendix 13.3. The incidence of non-serious AEs of special interest will be summarized by SOC and PT for each treatment group within each treatment cycle.

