Botulinum toxin A is considered first-line therapy for cervical dystonia, helping to improve pain, posture, and disability (Comella 2011, Simpson 2016, Mittal 2019). ABP-450 (prabotulinumtoxinA) is a toxin produced by *Clostridium botulinum*. It blocks neuromuscular transmission by binding to acceptor sites on motor nerve terminals, entering the nerve terminals, and inhibiting the release of acetylcholine. Blocking the release of acetylcholine plays a role in relaxing muscles by reducing muscle activity.

PrabotulinumtoxinA was evaluated in multiple non-clinical safety and toxicological tests to determine the pharmacologic and safety profile of the product in complying with International Council for Harmonisation of Technical Requirements for Pharmaceuticals for Human Use (ICH) guidelines/requirements for biologic products.

PrabotulinumtoxinA has also been found to be non-inferior to BOTOX[®] for the treatment of moderate to severe glabellar lines in adult patients and upper limb spasticity in patients with stroke (Nam 2015, Rzany 2019). The doses of ABP-450 used in the Phase 3 study for upper limb spasticity were similar to the doses of BOTOX[®] used (no significant differences were seen between the 2 groups) (Nam 2015).

ABP-19000 is an ongoing, Phase 2, randomized, double-blind, multicenter, placebo-controlled study to evaluate the safety and effectiveness of intramuscular ABP-450 injection for the treatment of cervical dystonia.

ABP-19002 is the open-label extension (OLE) study, wherein eligible patients from ABP-19000 studies, irrespective of treatment allocation, will have the option to continue treatment with ABP-450.

The ABP-19002 study will help to

evaluate safety and efficacy of repeat dosing of ABP-450 for the long-term treatment of cervical dystonia.

Clostridium botulinum toxins have become the standard of care for the treatment of patients with cervical dystonia, but also have significant risks associated with their use in these patients. The labels of marketed products carry prominent warnings concerning their side effects, such as dysphagia and even death, if they are not carefully administered and the patients are not monitored while under treatment. Even so, the benefit for all these products is greater than the potential risk.

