6.2.1.2 Serious Adverse Events

An SAE is defined as any event that

- results in death
- is immediately life-threatening
- requires inpatient hospitalization or prolongation of existing hospitalization
- results in persistent or significant disability/incapacity
- is a congenital anomaly/birth defect

Adverse events will be assessed from the time the patient signs the ICF until exit from the study (ie, 52 weeks or end of treatment [ET] after Day 0 "rollover").

Serious AEs that occur more than 56 days (ie, 8 weeks) after the last dose of investigational study drug and the patient has exited the study need not be reported unless the investigator considers them related to investigational study drug.

At every study visit, patients will be asked a standard non-leading question to elicit any medically related changes in their well-being. They will also be asked if they have been hospitalized, had any accidents, used any new medications, or changed concomitant medication regimens (both prescription and over-the-counter medications).

In addition to patient observations, AEs identified from any study data (eg, laboratory values, physical examination findings, changes in 12-lead ECG results) or identified from review of other documents that are relevant to patient safety will be documented on the AE page in the eCRF.

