6.2.1.5 Reporting Serious Adverse Events

Sponsor or its designee is responsible for reporting relevant SAEs to the competent authority, other applicable regulatory authorities, and participating investigators, in accordance with the ICH guidelines and/or local regulatory requirements.

The sponsor is responsible for reporting unexpected fatal or life-threatening events associated with the use of investigational study drug (expedited reports) to the regulatory agencies and competent authorities by telephone or fax within 7 calendar days after being notified of the event. The sponsor should report other relevant SAEs associated with the use of investigational study drug to the appropriate competent authorities (according to local guidelines), investigators, and the institutional review board (IRB) by a written safety report within 15 calendar days of notification.

6.2.1.6 Suspected Unexpected Serious Adverse Reactions and Non-Serious Adverse Events of Special Interest

The sponsor will promptly evaluate all suspected unexpected serious adverse reactions (SUSARs) and non-serious AEs of special interest against cumulative investigational study drug experience to identify and expeditiously communicate possible new safety findings to investigators, IRBs/independent ethics committees (IECs), and applicable health authorities based on applicable legislation.

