8.1.6. Serious Adverse Events

Treatment-emergent SAEs will be presented by SOC and PT in a manner similar to that described in Section 8.1. Incidence and frequency summaries and listings of all treatment-emergent SAEs will be presented for the SAF by treatment group in each treatment cycle, and across all cycles (by overall total doses of low, medium, and high).

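### SAP 8.1.10 counts only non-serious toxin-spread events, and no visible summary gives the number of patients with any such event

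*SAP*

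**What the plan says.** SAP 8.1.10 has two sentences. The first defines the group of events: "Adverse events potentially suggestive of distant spread of toxin effects are listed in Appendix 13.3". It sets no limit by seriousness. The second defines the summary and does set one: "The incidence of non-serious AEs of special interest will be summarized by SOC and PT for each treatment group within each treatment cycle". No total across cycles is stated there.

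The non-serious category also appears in Protocol 6.2.1.6, which deals with evaluating and communicating safety findings: "The sponsor will promptly evaluate all suspected unexpected serious adverse reactions (SUSARs) and non-serious AEs of special interest".

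Serious events have their own table in SAP 8.1.6: "Treatment-emergent SAEs will be presented by SOC and PT in a manner similar to that described in Section 8.1". That section adds a summary across all cycles by overall dose group. SAP 8.1.2 plans the all-TEAE table by SOC and PT on the same pattern, with serious and non-serious events together.

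**The concern.** The primary objective is the safety of repeat injections, and the Protocol's Introduction describes the class risk in strong terms: "The labels of marketed products carry prominent warnings concerning their side effects, such as dysphagia and even death". A reader who wants to know how many patients had signs of distant spread will go to the table built on the Appendix 13.3 list. As planned, that table leaves out the patients whose listed events were all serious, who matter most for this question.

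In Protocol 6.2.1.6 the split has a purpose, because serious events travel by the SAE route and only the non-serious ones need a separate instruction. Used as a filter on an incidence table, it serves no comparable purpose and cuts the group at its severe end. The descriptive summaries also carry more weight here than they might elsewhere. Protocol 6.4 and 11.1.1 plan neither an independent safety committee nor a data monitoring committee, and rely on monthly adverse-event reviews by the medical monitor and sponsor.

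**Working it through.** The documents give no event rate and no power calculation (SAP 4.3 plans no comparative analysis), so there is no figure of the plan's to reproduce. The check is of the text first and then of the possible size.

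**Step 1. Is a serious listed event outside the table?** Under Protocol 6.2.1.2 an event is serious if, among other criteria, it "requires inpatient hospitalization or prolongation of existing hospitalization". SAP 8.1.10 tabulates non-serious events. A listed event that leads to admission is therefore excluded by definition.

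**Step 2. Where else does that patient appear?**

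| Summary | Serious listed event included? | Toxin-spread grouping stated? | Across cycles? |
|---|---|---|---|
| SAP 8.1.2, all TEAEs | Yes, with non-serious, once per preferred term | No | Yes |
| SAP 8.1.5, severity | Yes, at worst severity | No | Not stated |
| SAP 8.1.6, SAEs | Yes | No | Yes |
| SAP 8.1.9, SUSARs | Only if not consistent with product information | No | Not stated |
| Protocol 7.5.1, primary analysis | Only if treatment-related and the patient was retreated | No | To Week 52 |
| SAP 8.1.10 | No | Yes | Not stated |

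All adverse events are also listed (SAP 8.1), and deaths have their own listing (SAP 8.1.11).

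**Step 3. Can the combined count be rebuilt from the visible tables?** For a single preferred term, yes: 8.1.2 gives the patient count with seriousness ignored. For the group as a whole, no. One patient may have several listed terms, so rows cannot be added. One patient may have both a serious and a non-serious listed event, so the 8.1.10 and 8.1.6 tables cannot be added either. Only the patient-level data give the total.

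**Step 4. Size.** For a given cycle and dose group, let T be the patients with at least one listed event, S those whose listed events there are all serious, and n the denominator. The planned filter counts T − S, so the shortfall is S/n. Because S cannot be negative, the table can understate but never overstate. A patient with both kinds of event is in T but not in S, and is still counted.

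The only sample sizes given are approximate possible enrolments: 59 (SAP 4.3) and 60 (Protocol 7.2). If an overall figure were formed, each serious-only patient would be worth 1/59 = 1.7 or 1/60 = 1.7 percentage points. The following counts are assumptions, with n = 59 and exact 95% intervals:

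| T | S | Any listed event | With the non-serious filter |
|---|---|---|---|
| 3 | 0 | 3/59 = 5.1% (1.1 to 14.1) | 3/59 = 5.1% (1.1 to 14.1) |
| 3 | 1 | 3/59 = 5.1% (1.1 to 14.1) | 2/59 = 3.4% (0.4 to 11.7) |
| 6 | 2 | 6/59 = 10.2% (3.8 to 20.8) | 4/59 = 6.8% (1.9 to 16.5) |
| 12 | 3 | 12/59 = 20.3% (11.0 to 32.8) | 9/59 = 15.3% (7.2 to 27.0) |

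Section 8.1.10 plans cells by dose group within cycle, not an overall row. If 59 patients were spread evenly over the three dose groups in a cycle (an assumption), a cell would hold 59/3 = 19.7 patients and one serious-only patient would be worth 1/19.7 = 5.1 points.

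The chance that at least one of 59 patients is serious-only is 1 − (1 − p)^59. For assumed p of 0.5%, 1%, 2% and 5% it is 26%, 45%, 70% and 95%.

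**The case against.** The strongest reply is that nothing is hidden. The heading and the sentence in 8.1.10 both say non-serious, so the table does not claim to give the total incidence of toxin spread. Serious events have a fuller table of their own, and 8.1.2 gives a complete, de-duplicated count for every preferred term. The study is open-label and descriptive, and no error rate or test depends on this summary.

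Most of that stands, and it rules out several stronger readings that a reader might infer:

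- **Serious toxin-spread events vanish from the report.** They do not. Step 2 shows where they appear; only the count across preferred terms is lacking.
- **8.1.10 is the only summary built on the list.** It is the only visible one. The item list in 8.1.2, section 8.1.3 and several figures in 8.1 are not shown, so a combined line cannot be ruled out.
- **Dysphagia admissions are left out.** Appendix 13.3 is not visible, so dysphagia is an example drawn from the class warnings and not a confirmed entry on the list.
- **The incidence is understated by some stated fraction, such as one third.** That depends wholly on assumed counts and on an overall denominator that 8.1.10 does not plan to show.
- **A dose group with worse events will show a lower rate.** The filter makes this possible, but nothing in the documents shows that it will happen.

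What the reply does not supply is a reason for the filter. The list is introduced without regard to seriousness, and the visible tables that include serious events state no grouping by it.

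**Conclusion.** The point holds in a limited form. SAP 8.1.10 omits patients whose only listed events in a cycle and dose group are serious, and no visible summary gives the number of patients with any listed event across preferred terms or across cycles. The error runs one way, and its size is the number of serious-only patients. That number may be zero, in which case the result is unchanged; the documents do not allow it to be estimated. The percentages in the working are illustrations on assumed counts.

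The conclusion assumes that Appendix 13.3 is not itself restricted by seriousness and that the text not shown holds no combined line. Confidence is moderate for that reason. The change is still worth making, because safety is the primary objective and the filter bears on the one visible summary of a named class risk.

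**What to change.** In SAP 8.1.10, summarise the number and percentage of patients with any treatment-emergent event on the Appendix 13.3 list, regardless of seriousness, with serious and non-serious sub-rows. Include a row that counts each patient once across preferred terms. Present it by treatment group within each cycle, and across all cycles by overall dose group, as 8.1.2 and 8.1.6 already do. Retitle the section to match. If such a line already exists elsewhere in the SAP, a cross-reference from 8.1.10 is enough.

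Leave the reporting route in Protocol 6.2.1.6 as it is. The cost is a short SAP edit and a changed table filter, with no new data.

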8.1.11. Death

A listing of patient deaths will be presented using the SAF.

8.2. Clinical Laboratory Evaluations

8.2.6. Urine Pregnancy Test

A urine pregnancy test will be performed as scheduled (see Appendix 13.1). Pregnancy test data will be provided in a listing.

_

9.1. Secondary Estimand

[figure not shown]
The secondary estimands for this study are:

[figure not shown]

9.1.1. TWSTRS Total Score

[figure not shown]
Most studies leading to the approval of currently available botulinum neurotoxins have used the TWSTRS scale as the primary efficacy measure (Espay 2018, Fernandez 2013). The standard TWSTRS is a comprehensive scale that comprises three subsets to assess motor severity, pain, and disability (Comella 2016). The motor severity subscale consists of 10 items, with variable scaling and weighting. It also includes a disability subscale with 6 items and a pain scale with 3 items. The total score is the sum of each of the subscales.

9.1.2. TWSTRS Subscale (Disability, Severity, and Pain) Scores

Summary statistics for TWSTRS subscale scores (actual subscale scores and change from baseline in TWSTRS subscale score to each scheduled post baseline visit) will be calculated

[figure not shown]

9.1.4. PGI-C

The PGI-C enables the patient to rate changes in their perception of their general health status over the duration of the assessment via a 7-point scale ranging from "very much improved" to "very much worse" (Fischer 1999). Detailed descriptions of the PGI-C are provided in study protocol Section 13.4. PGI-C scores will be measured as per scheduled of assessment (see Appendix 13.1).

Summary statistics for actual PGI-C scores at each scheduled post baseline visit will be calculated as described for continuous variables in section 4.1.

[figure not shown]
9.1.6. CGI-C

The CGI-C is a 7-point scale ranging from "very much improved" to "very much worse" (Guy 1976) based on the physician's perception of the patient's health status. Detailed descriptions of the CGI-C are provided in study protocol section 13.5 and CGI-C scores will be measured as per scheduled of assessment (see Appendix 13.1).

Summary statistics for actual CGI-C scores at each scheduled post baseline visit will be calculated as described for continuous variables in Section 4.1.

9.1.7. Time to loss of 80% peak treatment effect of TWSTRS Total Score.

[figure not shown]
Summary statistics for time to loss of $\ge 80\%$ of peak treatment effect for patients dosed on ABP-450 will be tabulated by treatment cycle and treatment group.

[figure not shown]
10. Interim Analysis

There is no planned interim analysis for this OLE study.

11. Changes in the Planned Analysis

12. References

Statistical Analysis Plan, Version 2.0 Date Issued: 24Aug2023.

13. Appendices

Aeon Biopharma, Inc ABP-19002 (Version 2.1) 13MAY2021 Statistical Analysis Plan, Version 2.0 Date Issued: 24Aug2023.

Aeon Biopharma, Inc ABP-19002 (Version 2.1) 13MAY2021 Statistical Analysis Plan, Version 2.0 Date Issued: 24Aug2023.
